#### **Population**:

Patients 18 to 70 years old with newly diagnosed GBM (Grade 4 astrocytoma), who will undergo surgery, are eligible to enter into screening. Patients in screening who have received external beam radiation therapy with concurrent temozolomide chemotherapy according to the Stupp protocol guidelines (Stupp et al., N Engl J Med 352: 987-96, 2005), without evidence of disease progression following radiation therapy, are eligible to be randomized into the study. All patients must have a Karnofsky Performance Score (KPS) of ≥70, ≥8 week life expectancy, no other prior malignancy within the last 5 years, and no active infections. See section 7 for full eligibility criteria.

#### **Treatment Schedule:**

Two intradermal (i.d.) injections of DCVax-L (active) or autologous MNC (placebo) per treatment; each injection consisting of 1.25 million DC in approximately 0.15 mL, in the upper arm. Injection volume is patient specific and the Certificate of Analysis (C of A) should be referenced. Treatments will be given at days 0, 10, 20, and at months 2, 4, 8, 12, 18, 24 and 30. All Crossover patients will receive the active immunization injections on this schedule, study drug supply availability permitting.

#### **Efficacy Assessments:**

Disease progression is assessed every 2 months by central review of brain MRI scans, according to the imaging parameters in the imaging manual. KPS is assessed every 2 months during clinic visits. Immune monitoring labs are drawn at regular intervals throughout the treatment period.

#### Primary Endpoint and Secondary Endpoint, Hypotheses, and Analytic Method

Primary: The primary objective of this study is to compare overall survival (OS) between patients randomized to DCVax-L and control patients from comparable, contemporaneous trials who received standard of care therapy only, in patients with newly diagnosed glioblastoma.

Hypothesis: Overall survival, measured from time of randomization, will be longer for patients in the DCVax-L cohort compared to patients who received standard of care in other, comparable, contemporaneous trials.

Analytic Method #1: Proportional hazards (Cox) regression.

Analytic Method #2: Conditional Survival analysis

Analytic Method #3: Overall Survival in specific subgroups

**Secondary**: The first secondary objective is to compare overall survival (OS) between patients randomized to placebo who received DCVax-L treatment following disease recurrence, and control patients from comparable, contemporaneous clinical trials, in patients with recurrent GBM.

Hypothesis: Overall survival, measured from time of disease progression, will be longer for patients in the placebo cohort who received treatment with DCVax-L upon disease progression, when compared to control patients from other comparable contemporaneous clinical trials who received best available care.

Analytic Method: Cox regression.

**Secondary**: The second secondary objective, confirmed progression-free survival (cPFS), is to compare confirmed disease progression (cPD) between subjects randomized to DCVax®-L and those randomized to Placebo within Study 020221.

Protocol: 020221, v7.0 23SEP2020 Page 3 of 55

Northwest Biotherapeutics, Inc. DCVax®-L, IND #10206

**Secondary**: The third secondary objective, PFS, is to compare progression-free survival between subjects randomized to DCVax®-L and those randomized to Placebo within Study 020221.

**Secondary**: The fourth secondary objective, OS, is to compare overall survival between subjects randomized to DCVax®-L and those randomized to Placebo within Study 020221.

**Secondary**: The fifth secondary objective is to compare tumor response between subjects randomized to DCVax®-L and those randomized to Placebo within Study 020221.

#### **Other Endpoints**

- To compare the following between subjects in the DCVax®-L arm and subjects in the placebo arm within the Trial:
- Immune profiles in the peripheral blood that may be predictive of response/non-response to immunotherapies
- Decline in physical functioning, measured by Karnofsky Performance Status (KPS) evaluation
- Time to progression of disease (TTP)
- Survival at 6, 12, 18, 24, 30, 36, 42, 48, 54 and 60 months
- Times to PFS, OS and TTP, measured from initial surgery.

To evaluate further the safety profile of DCVax®-L.

Protocol: 020221, v7.0 23SEP2020 Page 4 of 55

Northwest Biotherapeutics, Inc.

DCVax®-L

Protocol 020221, Version 6.2

A Phase III Clinical Trial Evaluating DCVax®-L, Autologous Dendritic Cells Pulsed with Tumor Lysate Antigen for the Treatment of Glioblastoma Multiforme

Protocol: 020221, v7.0 23SEP2020 Page 5 of 55

#### 1. GENERAL INFORMATION

#### 1.1. PROTOCOL TITLE

A Phase III Clinical Trial Evaluating DCVax®-L, Autologous Dendritic Cells Pulsed with Tumor Lysate Antigen for the Treatment of Glioblastoma Multiforme

#### 1.4. INVESTIGATOR INFORMATION

A list of Investigators and sites participating in this study is on file at NWBT.

#### 1.5. CONTRACTORS AND CONSULTANTS FOR THE STUDY

See Appendix G.

#### 2. INTRODUCTION TO THE PROTOCOL

#### 2.1. INTRODUCTION

DCVax-L was used in a Phase I/II clinical trial to immunize patients with GBM (Grade 4 astrocytoma), following primary therapy that consisted of surgery, followed by conventional external beam radiation and temozolomide chemotherapy during radiation and for six cycles after radiation. No serious adverse events (SAE) attributable to the study drug were observed. Based on promising data in patients with GBM indicating slowing of disease progression and increased survival, the following Phase III study, which is designed as a pivotal study, will be conducted in patients presenting with newly diagnosed GBM.

#### 2.2. PHASE I/II CLINICAL TRIALS

The results of the Phase I/II trials to test the safety and efficacy of DCVax-L are briefly summarized below, and are more fully described in the accompanying Investigator's Brochure (IB). There is an abundance of cancer literature supporting the safety and potential efficacy of using autologous DC pulsed with autologous tumor lysate antigen, in which 43 trials involving 903 patients are described, with no evidence of serious toxicities or autoimmunity (see IB for a complete listing of references).

The Phase III protocol is predicated on two Phase I/II trials (BB-IND #8434 and #11053) carried out by [name] and [name] at the University of California, Los Angeles (UCLA).

Twenty (20) patients with newly diagnosed GBM have been enrolled in 2 Phase I/II trials (data as of June 2011). Patients have been followed for up to 10 years. Sixteen patients have surpassed the historical median time to progression (TTP) of 8.9 months, without evidence of disease progression. Overall, 16 patients have progressed; the four patients with no progression of disease have follow-up times ranging from 43 to 122 months from surgery; these are also the only 4 patients who

Protocol: 020221, v7.0 23SEP2020

are still alive. Median progression free survival in these 20 patients is 26.4 months (when McDonald's criteria are used), and median survival time is 35 months. Historically, at the same institution (UCLA), patients similar to those enrolled in the trial (R.P.A. classes III and IV) have median times to disease progression of 8.9 months (± 7.3 months), and median survival times of 15 months (± 13.9 months).

In a multicenter trial, 287 patients treated post surgery with radiotherapy plus concomitant temozolomide achieved median progression free survival (PFS) of 6.9 months from surgery (95% confidence interval, 5.8 to 8.2) and median survival of 14.6 months from surgery (95% confidence interval, 13.3 to 16.8; Stupp, 2005). In the Phase II trial, PFS and survival times will be calculated from time of randomization, which is expected to occur approximately three months after initial surgery.

Adverse events: To date, there have been no serious adverse events related to the study drug. Non-serious adverse events including mild symptoms of nausea/vomiting, headache, fatigue, diarrhea, low-grade fever and loss of appetite were the most common symptoms that could possibly or likely be associated with the treatment. Lymph node swelling, myalgia, arthralgia, back/neck pain, depression, dehydration, hiccoughs, dizziness, cough, somnolence, dyspnea, allergic rhinitis, and pain/itching at injection site were other less common symptoms reported. Most AEs and all SAEs were deemed related to disease progression.

#### 3. OVERVIEW OF DCVAX-L PHASE III CLINICAL TRIAL

This protocol describes a randomized, placebo-controlled, double blinded, multi-center, multi-national Phase III clinical trial for DCVax-L in patients with newly diagnosed GBM (DCVax-L, when used for primary brain cancer, is sometimes referred to as DCVax-Brain). The primary endpoint for the study is Overall Survival compared to external controls. The study is powered to detect meaningful clinical benefit for this . Secondary endpoints include survival in patients with disease recurrence compared to external controls, confirmed progression-free survival, and tumor response, as well as the original trial endpoints PFS and OS. Other (tertiary) endpoints include time to progression (TTP), decline in Karnofsky Performance Status (KPS), landmark analyses of survival, and immune responses to DCVax-L.

The underlying hypothesis is that DCVax-L, i.e. DC generated from the peripheral blood of a patient with GBM and loaded (combined) with tumor lysate antigen, will safely (1) delay time to disease progression, (2) increase survival and (3) induce anti-tumor immunity when administered as a series of intradermal (i.d.) injections in newly diagnosed patients. DCVax-L is intended as adjuvant therapy to standard primary treatments, which include surgical resection, external beam radiation therapy with concurrent temozolomide chemotherapy, followed by additional cycles of temozolomide chemotherapy essentially following the protocol guidelines according to Stupp et al. (N Engl J Med 352: 987-96, 2005; "The Stupp Protocol"). Administration of adjuvant temozolomide is minimally modified from the guidelines to allow for vaccine dose window adherence.

Protocol: 020221, v7.0 23SEP2020 Page 10 of 55

#### 3.1. OBJECTIVES

#### 3.1.1. Primary objective

The primary objective of this study is to compare overall survival (OS) between patients randomized to DCVax-L and control patients from comparable, contemporaneous trials who received standard of care therapy only, in patients with newly diagnosed glioblastoma.

Hypothesis: Overall survival, measured from time of randomization, will be longer for patients in the DCVax-L cohort compared to patients who received standard of care in other, comparable, contemporaneous clinical trials.

Analytic Method #1: Proportional hazards (Cox) regression.

Analytic Method #2: Conditional survival analysis

Analytic Method #3: Overall survival in specific subgroups

#### 3.1.2. Secondary objective

The first secondary objective is to compare overall survival (OS) between patients randomized to placebo who received DCVax-L treatment following disease recurrence, and control patients from comparable, contemporaneous clinical trials, in patients with recurrent GBM.

The second secondary objective, confirmed progression-free survival (cPFS), is to compare confirmed disease progression (cPD) between subjects randomized to DCVax®-L and those randomized to Placebo within Study 020221.

The third secondary objective, PFS, is to compare progression-free survival between subjects randomized to DCVax®-L and those randomized to Placebo within Study 020221.

The fourth secondary objective, OS, is to compare overall survival between subjects randomized to DCVax®-L and those randomized to Placebo within Study 020221.

The fifth secondary objective tumor response, is to compare tumor response rates between subjects randomized to DCVax®-L and those randomized to Placebo within Study 020221.

#### 3.1.3. Tertiary objectives

- To compare immune responses between patients in the treatment cohort and patients in the placebo cohort for all randomized patients (i.e., patients randomized at baseline with no evidence of disease progression); The percentage of patients mounting a T cell response to tumor antigens is expected to be higher in patients immunized with DCVax-L when compared to patients immunized with the placebo;
- To compare decline in physical functioning, measured by KPS evaluation, between patients in the treatment cohort and patients in the placebo cohort for all randomized patients (i.e., patients randomized at baseline with no evidence of disease progression). Patients in the treatment cohort are expected to experience a slower rate of decline in physical functioning than patients in the placebo cohort.;

Protocol: 020221, v7.0 23SEP2020 Page 11 of 55

- To compare time to progression of disease (TTP; includes as events all radiographic evidence of disease progression; all deaths are censored) between patients in the treatment cohort and patients in the placebo cohort for all randomized patients (i.e., patients randomized at baseline with no evidence of disease progression). TTP is expected to be longer for patients in the treatment cohort than for patients in the placebo cohort.;
- To compare survival at 6, 12, 18, 24, 36 and 48 months between patients in the treatment cohort and patients in the placebo cohort for all randomized patients (i.e., patients randomized at baseline with no evidence of disease progression). The percentage of patients surviving at these time points is expected to be greater in the treatment cohort than in the placebo cohort.

#### 3.1.4. Safety objective

To evaluate further the safety of DCVax-L.

#### 3.2. STUDY POPULATION

Patients with newly diagnosed GBM are eligible for this protocol. Diagnosis of GBM will be confirmed through independent central pathology review. Patients must have a surgically accessible, unilateral tumor for which surgical resection, with intent to perform a gross total **or** near gross total resection, is indicated.

#### 3.3. STUDY DESIGN

The study is designed as a randomized, placebo-controlled, double blinded, multi-center, multi-national Phase III clinical trial, with a crossover option for all patients who have progressed.

Approximately 348 patients with newly diagnosed GBM, and with no evidence of disease progression at Baseline will be randomized 2:1 (232 into the treatment cohort and 116 into the placebo-cohort). All patients will receive standard treatment consisting of: a) surgical resection, b) external beam radiation with concurrent chemotherapy (temozolomide), and followed by additional 28-day cycles of temozolomide chemotherapy (see Appendix C for details).

Patients with evidence of progressive disease (as determined by central radiology review) post radiation therapy with concomitant temozolomide chemotherapy are not eligible for this study.

The study schedule anticipates an approximate active enrollment period of 36 months. An initial efficacy analysis for the primary endpoint (PFS) in patients with no evidence of disease progression at Baseline will be performed after approximately 248 events (progression or death) have occurred in the treated patients and the placebo controls combined, which is expected to occur approximately 5 months after enrollment of the last patient.

All patients in the study will be followed for the collection of data on late progression and vital status until a total of 233 deaths have occurred in the treatment and placebo cohorts combined, which is expected to occur approximately 36 months after completion of enrollment. Schematics of the study timeline are presented in Appendix A, and a detailed overview of the timeline following radiation therapy is provided in Appendix B.

All randomized patients receive up to 10 immunizations of DCVax-L or autologous MNC (placebo cohort) at days 0, 10, 20, and at months 2, 4, 8, 12, 18, 24 and 30) following recovery from surgery and radiation with concurrent temozolomide chemotherapy. All visits, including immunization dates, are calculated from day 0 (the date of the first immunization), and for the purposes of this protocol, a 28-day month is used for calculating visits. Some patients may not receive 10 immunizations due to insufficient material; in these cases immunizations will be replaced with placebo while maintaining the blind. Patients who elect to receive DCVax-L immunizations post confirmed disease progression and crossover will restart the immunization schedule and may receive a total of more than 10 immunizations during the course of the study.

For each immunization, patients will receive two intradermal injections (i.d.) of approximately 150µl (0.15mL) containing 1.25 million cells each (DCVax-L or MNC) in an outpatient setting. Injection volume is patient specific and the Certificate of Analysis (C of A) should be referenced. Patients are observed for acute toxicity every 30 minutes for 2 hours post-injection.

#### 3.4. ESTIMATED ACCRUAL

It is estimated that accrual will range from 0.1 - 2 participants per month per site, at approximately 90 clinical sites participating in the study. Approximately 348 patients will be randomized into the study to test the primary and secondary hypotheses.

#### 3.5. NAME OF SPONSOR/FUNDING SOURCE

Northwest Biotherapeutics, Inc.

#### 4. SAFETY CONSIDERATIONS

The major component of DCVax-L is autologous DC loaded with autologous tumor lysate antigen. DC are generated by *ex vivo* culturing of adherent peripheral blood monocytes with the cytokines granulocyte-macrophage colony stimulating factor (GM-CSF) and interleukin-4 (IL-4) for 5-7 days. DC are harvested, loaded with tumor lysate antigen, washed extensively, and cryopreserved as DCVax-L. After washing, only trace amounts of GM-CSF, IL-4, and unloaded antigenic material are introduced into the patient. For each immunization, two vials containing DCVax-L are thawed and two injections of approximately 150µl each are given i.d.

Autologous MNC are purified directly from a leukapheresis through density gradient centrifugation, and contain no foreign substances other than the diluent and cryopreservative.

The Phase III clinical trial is predicated on a Phase I/II clinical trial carried out at UCLA (BB-IND #11053). No Grade 3 or 4 toxicities related to the treatment were observed in this trial, leading to the preliminary conclusion that DCVax-L is safe to administer to patients with brain cancer.

There are a number of published studies referring to similar therapies that have utilized *ex vivo* manipulated autologous DC pulsed with autologous tumor lysate. No serious toxicities or clinically meaningful evidence of autoimmunity were observed in 43 trials comprising a total of 770 patients (fully referenced in accompanying Investigator's Brochure).

#### 5. BRIEF DESCRIPTION OF MANUFACTURING PROCESS FOR DCVAX-L

Both DCVax-L and the placebo will be manufactured for all patients undergoing leukapheresis.

**REDACTED** 

Protocol: 020221, v7.0 23SEP2020 Page 13 of 55

#### 6. BRIEF DESCRIPTION OF MANUFACTURING PROCESS FOR PLACEBO

(Both DCVax-L and placebo will be manufactured for all patients undergoing leukapheresis.)

#### **REDACTED**

#### 7. PATIENT ELIGIBILITY

#### 7.1. INCLUSION CRITERIA

All patients, unless specified otherwise below, must meet the following inclusion criteria at the indicated time points.

#### Determined at pre-screening

- Patients ≥18 and ≤70 years of age at surgery
- Patients must be able to understand and sign the Informed Consent indicating that
  they are aware of the investigational nature of this study. The consent for tumor
  donation may be signed by a legally authorized representative (LAR) if allowed by
  the institution.
- Patients must have a life expectancy of ≥8 weeks

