**Benefit** 

Job Number: 1555

characteristics include the methylation status of the MGMT gene in the tumor, IDH mutation status, extent of surgical resection of the tumor, and others. As explained above, in this SAP a portion of the statistical alpha is separately assigned to analysis of pre-specified sub-groups. This alpha will be applied to the first sub-group analysis. After the first one, additional sub-group analyses will be conducted in a hierarchy – i.e., each successive sub-group analysis after the first one will be reached if the one before it is positive. The first sub-group analysis will be survival in patients with methylated MGMT gene. Thereafter, additional analyses will include, minimal residual disease, age <65, significant residual disease, unmethylated MGMT, and age ≥ 65.

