# 8.1 Statistical methods for the analysis of the primary endpoints: comparison with external study control groups

#### 8.1.1 Type I error for the Primary Endpoints

The overall one-sided type I error for the study was set at 2.5%. One of the two planned interim efficacy analysis was conducted in March 2015 after 56.4% of subjects had completed 6 months follow up. The O'Brien-Fleming one-sided alpha level for the final analysis (i.e. the stage 2 alpha level) is 2.409%.

Final testing for the three analyses of the primary endpoint will follow an alpha-exhaustive, fallback procedure [8].

An alpha level of 2% will be used with OS, 0.309% will be used with CS and the remaining 0.1% will be used for the analysis of OS in the pre-specified subgroups. The testing will proceed as presented in Figure 3 (below); in this way, the family-wise error rate is preserved at 2.409% for the primary endpoints.

The additional pre-specified subgroup analyses will be conducted in order, at the same alpha level as for the MGMT methylated subgroup, as follows.

[figure not shown]
- 2. Extent of resection: Minimal residual disease
- 3. Age < 65
- MGMT unmethylated
- 5. Extent of resection: Significant residual disease
- 6. Age ≥ 65

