#### 8.1.3 External studies in newly diagnosed GBM

A systematic literature review has been conducted by independent experts to identify appropriate studies in newly diagnosed GBM to provide the external controls. This selection of studies has subsequently been reviewed by independent key opinion leaders in the field who were not involved in conducting the Trial, and has received their support. The five studies shown in Table 3 [6, 13-16], which were conducted in similar populations as in the current Phase III study, each with a control arm treated with the standard radiotherapy and temozolomide regimen, will be included. It is possible that additional studies may be added, e.g. with the goal to provide a larger population of patients with long (e.g.  $\geq$  4 years) follow-up times. In addition, a MAIC will be undertaken to ensure matching of the Trial subjects and the external controls.

It is recognized that each of these studies had unique inclusion and exclusion criteria, and that no single study can provide a perfectly matched control population. Nevertheless, the distribution of known prognostic factors between the enrolled patient populations reveal that these populations were similar in composition, and in fact the study outcomes are also remarkably similar: These five studies selected by the independent expert review provide 1,366 patients for the combined control group in total.

Median overall survival for these 1,366 patients is 16.5 months, with a 95% confidence interval of 16.0 to 17.5 months, demonstrating that outcome in this disease is highly consistent and predictable.

The Gilbert et al. (2014) study randomized patients 3 weeks prior to completion of chemoradiation therapy, and if that study is excluded from the analyses the outcomes of the control subjects are as follows: n=1,057; mOS=16.8 months (95% CI: 16.1-17.7 months).

Page 33 of 57 Confidential

Table 3: Studies selected providing comparable control arms

[figure not shown]
Lead	Year	Journal	CONT	ROL GROUP		
author			Treatment	N	Median OS (months)	OS Kaplan-Meier curves available for subgroups
Gilbert	2013	JCO	XRT + temozolomide	411	16.6	MGMT methylated (N = 122), unmethylated (N = 254)
Stupp	2017	JAMA	XRT + temozolomide	229	16.0	Age < 65y (N = 184), Age ≥ 65 y (N = 45),  MGMT methylated (N = 77),  unmethylated (N = 95)
Weller	2017	Lancet oncology	XRT + temozolomide	374	17.4	Minimal residual disease N = 210), Significant residual disease (N = 163)

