#### Sensitivity analysis 1: Matching-adjusted indirect comparison (MAIC), external studies pooled

A matching-adjusted indirect comparison (MAIC) will be used to compare the treatment groups. The MAIC technique is explained in detail in Appendix D.

Overall survival

The MAIC will be adjusted for the following characteristics.

Table 4: Characteristics to be matched via MAIC: selected studies

Characteristic	Number of studies	Cate	gories
MGMT methylation status	5	methylated	unmethylated
Performance status (KPS)	4	< 90%	>= 90%
Surgical status	4	Complete resection / minimal residual disease	Incomplete resection / significant residual disease
Sex	5	M	F
Race	4	White	Non-white
Age	5	Continuous	

The numbers of subjects in each subgroup will be calculated for each study where the information is available. For factors where the information is available for all external studies, the overall proportions across all 1,366 subjects can then be calculated. For factors recorded in only four out of the five studies, the proportion of subjects in those studies will be applied to all the 1,366 subjects for the purposes of matching.

For the pooled published studies, the reconstructed IPD will be compared to the weighted data resulting from matching (see Appendix D) from the DCVax®-L subjects. A Cox proportional hazards model will be used to estimate the treatment effect in the form of a hazard ratio.

Kaplan-Meier estimates of the survival functions for the weighted DCVax®-L population and the comparator population will be plotted and estimates of survival to 6, 12, 18, 24, 30, 36, 42, 48, 54 and 60 months will be calculated (with 95% confidence intervals).

Survival conditional on survival to M months

Conditional survival analysis using MAIC weights will not be feasible using published data, but will be conducted if original individual patient data are available.

Overall survival for subgroups

It may not be feasible to analyse survival in subgroups using the MAIC approach if the proportions of subjects with the relevant characteristics are not known for the subgroups unless the original data is available from comparator studies. If such data is available, this analysis will be conducted.

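### The alpha-carrying 'Age ≥ 65' step compares DCVax-L patients aged about 65-70 with one published control curve that has no stated upper age, so a bias in favour of DCVax-L cannot be excluded

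*Combined protocol and SAP*

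**What the plan says.** **Eligibility.** The inclusion criteria in protocol section 7.1 require "Patients ≥18 and ≤70 years of age at surgery". The synopsis repeats the limit under Population: "Patients 18 to 70 years old with newly diagnosed GBM (Grade 4 astrocytoma), who will undergo surgery, are eligible to enter into screening".

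**Status of the subgroup.** SAP section 1.2.1 (Analysis #3) puts survival in MGMT-methylated patients first and then lists the rest: "Thereafter, additional analyses will include, minimal residual disease, age <65, significant residual disease, unmethylated MGMT, and age ≥ 65". Section 8.1.1 assigns alpha to this chain: "the remaining 0.1% will be used for the analysis of OS in the pre-specified subgroups". On the later subgroups it adds: "The additional pre-specified subgroup analyses will be conducted in order, at the same alpha level as for the MGMT methylated subgroup, as follows". The split is said to ensure that "the family-wise error rate is preserved at 2.409% for the primary endpoints".

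**Control data.** In Table 3 (section 8.1.3) only the tumor-treating-fields trial offers survival curves by age: "Age < 65y (N = 184), Age ≥ 65 y (N = 45"). No upper age is given for the older group.

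**Method.** Section 8.1.5 reconstructs survival times from the digitised subgroup curve and fits a simple proportional hazards model without covariates. This analysis covers all selected studies, whether or not their original data were also obtained. On matching within subgroups, Sensitivity analysis 1 says: "It may not be feasible to analyse survival in subgroups using the MAIC approach". Both MAIC sensitivity analyses commit to subgroup matching only if original data become available. Section 8.1.4 allows covariates, as available, under the same condition.

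**The concern.** Splitting by age should make the treated and control groups more alike in age. Here the treated stratum is closed near 70, while the control stratum, as labelled, is open. The SAP (section 1 and the opening of section 6) names age as a known prognostic factor. Section 8.1.3 concedes in general terms that the external trials had their own eligibility criteria, but no passage mentions the age cap or aligns the controls to it.

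If some of the 45 controls are over 70, they have no DCVax-L counterpart, and their presumably worse prognosis would be read as a treatment effect. The imbalance can run only one way, and it would sit inside a test that carries alpha under the primary endpoint. Separately, 'Age ≥ 65' describes the treated group loosely whatever the control ages are.

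**Working it through.** **1. The plan's own figures.**
- 184 + 45 = 229, the whole control arm of the tumor-treating-fields trial in Table 3. No other listed study has age curves, so the 45 are the only identified control.
- 2 + 0.309 + 0.1 = 2.409%, the stated one-sided total.

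**2. Alpha at the step.** The chain starts at 0.1%. Section 8.1.1 names an alpha-exhaustive fallback procedure, so if OS and conditional survival have both been rejected the chain should hold the full 2.409%. This is inferred from the named procedure, because Figure 3 is not legible in the text reviewed. Both levels are carried below.

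**3. What cannot be computed.** The documents give neither the number of DCVax-L patients aged 65-70 nor the ages of the 45 controls. The rest is illustration.

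**4. Analytic illustration, no treatment effect.**

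Assumptions: control ages normal, SD 9 to 12; no upper age limit in the control trial; treated ages 65 up to 71.0 (70 in completed years); hazard ratio per decade of age h = 1.3 to 1.8; treated number n = 30 to 40; 90% of treated patients and 85% of controls die. The only input from the documents is the share aged 65 or over, 45/229 = 0.1965, for which z = 0.854. The control mean is then 65 − 0.854 × SD.

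| SD | Control mean age | Share of the 45 over 70 | Mean age, 65+ uncapped | Mean age, 65 to <71 | Gap d (years) |
|---|---|---|---|---|---|
| 9 | 57.3 | 33% (about 15) | 70.0 | 67.6 | 2.4 |
| 12 | 54.8 | 45% (about 20) | 71.7 | 67.7 | 3.9 |

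Spurious hazard ratio = h^(−d/10):
- smallest: 1.3^(−0.239) = 0.94
- largest: 1.8^(−0.394) = 0.79

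SE of the log hazard ratio = √[1/(0.9n) + 1/(0.85 × 45)], which is 0.251 for n = 30 and 0.232 for n = 40.

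False-positive rate = P(Z > z_α − |log HR|/SE), with z_α = 1.976 at 2.409% and 3.090 at 0.1%:
- smallest (log HR −0.063, n = 30): 4.2% at 2.409%; 0.2% at 0.1%
- largest (log HR −0.231, n = 40): 16.4% at 2.409%; 1.8% at 0.1%

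With the treated ceiling at exactly 70.0 instead, 40-52% of controls lie above it, the gap is 2.8-4.4 years, and the rate at 2.409% reaches 19%.

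**5. Simulation on different assumptions.** Log-rank test, no treatment effect, 6,000 runs per setting; exponential survival with median 14 months at 65-70; 35 to 58 treated patients (15-25% of 232); follow-up 60 months treated and 36 months control; hazard ratio for over-70 against 65-70 of 1.25 to 2.0.

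| Controls over 70 | Apparent HR | False positives at 2.409% | At 0.1% |
|---|---|---|---|
| 0% | 0.99-1.01 | 1.7-3.0% | 0.05-0.15% |
| 25% | 0.95-0.85 | 4-11% | 0.2-0.9% |
| 50% | 0.90-0.72 | 7-32% | 0.4-5.8% |

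The direction agrees with step 4. With no controls over 70 the bias vanishes. The size depends on the assumptions.

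**6. Which age.** The cap applies at surgery. Protocol section 2.2 expects randomization about three months later, so a few patients may be 71 by then. SAP section 8.3.4 takes age at randomization as a covariate, but no passage says which age defines this subgroup.

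**The case against.** The strongest reply is that no bias has been shown. It needs controls over 70, and the documents give neither an age limit nor an age distribution for that trial. This stands: the mismatch is unexcluded, not demonstrated, and apart from 45/229 every input to the illustration is an outside assumption.

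Second, the step has little practical weight. It is last in sections 1.2.1 and 8.1.1 and fifth in 8.1.5, so it is tested only after four or five earlier subgroups, including Age < 65, have all succeeded. This also stands. A reader might take 4-16% as the study's chance of a false claim; it is the error rate given that the step is reached and tested at 2.409%.

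Third, the plan partly provides for the problem: with original data, sections 8.1.4 and 8.1.5 allow covariates and subgroup matching. That is true, but getting the data is not assured, the unadjusted published-data analysis runs regardless, and nothing confines the controls to 70 or under.

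Fourth, 'Age ≥ 65' is only a category name, bounded by the eligibility rule. A reader might infer that success here would be claimed for patients over 70. No passage says so, and the 18-70 limit is explicit in the protocol to which the SAP is appended. The label is imprecise and nothing more.

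**Conclusion.** The concern holds as a comparability gap in one late alpha-carrying step. The treated patients are about 65-70, the sole identified control group has no stated upper age, and the published-data test does not adjust for age. Any resulting bias would favour DCVax-L. Under the analytic assumptions, an inactive treatment would show a hazard ratio of 0.94 to 0.79, with false-positive rates of about 4-16% at 2.409% or 0.2-1.8% at 0.1%, conditional on reaching the step. If the control trial also stopped at 70, the bias is zero and only the label needs correcting.

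A reader might infer that every OS analysis using original data should exclude controls over 70. The material here bears on this one subgroup and does not support that wider demand. The point is a cheap improvement of low priority.

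**What to change.** - In SAP sections 8.1.1 and 8.1.5, define the subgroup as age 65-70 in both groups, state the date at which age is taken (surgery or randomization), and label any result 65-70.
- Find and state the upper age limit of the comparator trial.
- Keep the step in the alpha chain only if its controls are all 70 or under, or can be restricted to that range with the original data already being requested under section 8.1.3. Otherwise report the comparison descriptively, outside the chain.

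The cost is a change of SAP wording. The downside is that one of the last steps of the chain may become descriptive, and a few controls are lost if the data are cut at 70.
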